**b. Safety monitoring**

The principal investigator is responsible for data and safety monitoring. If study staff becomes aware of any adverse events, the event will be reported immediately to the PI.

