**V. STUDY PROCEDURES**

**a. Study visits and parameters to be measured**

*Adapted MBCT intervention*

The MBCT intervention is based on Mindfulness-Based Cognitive Therapy (MBCT), an evidence-based, manualized protocol for treating depression symptoms. We have developed an adapted MBCT protocol based on our preliminary qualitative work and open pilot trial and continue to make iterative refinements based on patient feedback. Participants randomized to the MBCT intervention will be expected to participate in 8-weekly virtual sessions, in conjunction with approximately 30 minutes of at-home daily practice. Each weekly virtual session will last approximately 1.5 hours. A licensed mental health provider (e.g., LICSW, PhD) trained in the MBCT protocol will deliver the

intervention. The interventionist will receive ongoing supervision and feedback from the PI or MBCT mentor. The MBCT intervention will not be delivered clinically; it is a psycho-educational intervention. We will also send audio recordings used for home mindfulness practice via Partners email (send secure or unencrypted if the patient prefers).

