**e. Data to be collected and when the data is to be collected**

The self-report survey measures will be the same for the MBCT and control groups. The surveys will be administered within approximately 1-2 weeks before and after the intervention and at 3 months post-intervention. This battery will include the following validated self-report surveys: Assessment of Survivor Concerns (fear of recurrence), CAMS-R (mindfulness), Cardiac History and Symptoms, Current Experiences Scale (CES; resiliency), COVID items, demographic questionnaire, Expectancy Questionnaire, Experiences Questionnaire (decentering), Group cohesion scale, Hospital Anxiety and Depression Scale (HADS; depression and anxiety), Interpersonal Reactivity Index (IRI; empathy), MAIA-2 body subscales (interoception), MBCT-AS Checklist (fidelity checklist), PHQ-9 (depression), Medical Outcomes Study – Specific Adherence Scale (MOS-SAS; health behaviors), one item from the Short Form-12 (SF-12), Self-Other Four Immeasurables (SOFI; self and other compassion), PROMIS Physical Function (PROMIS-PF; physical function), and The Positive and Negative Affect Schedule-Positive Affect (PANAS-PA). The post-intervention survey will also include a group cohesiveness measures to assess perceived connection with other group members as well as intervention satisfaction questions to assess acceptability. The 3-month follow-up survey will include questions about continued mindfulness practice. The baseline survey, post-intervention survey and post-intervention survey will all include questions related to COVID-19. All three survey batteries are included in the IRB submission.

At the end of each session all participations will complete a post-session survey assessing session likes and dislikes. Between each session intervention participants will be asked to complete home practice logs documenting the frequency of and the thoughts related to their weekly mindfulness practice.

Upon completion of the intervention, participants from both the intervention and control group will be asked to complete a 30-60-minute exit interview via phone or videoconference.

Both intervention and control group participants will be asked to provide dried blood spot samples within one week before and after the intervention and 3-months-post intervention. Samples will be used to examine IL-6, CRP, and TNF- $\alpha$  levels.

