specific instructions at each step based on the patients' response. It begins by clarifying the response to PHQ-9 item 9 (i.e., determining passive versus active suicidality). If patients endorse active suicidality, the RA will further assess safety risks (e.g., plan, intent, past suicide attempts) and immediately notify the PI (a licensed clinical psychologist) to conduct further assessment. The PI will conduct detailed suicide assessment of patients with active suicidality and inform the patient's primary treatment providers of the patient's symptoms and assist with the obtainment of further evaluation and care as needed (e.g., through referral to outpatient treatment or to the emergency department [ED]), depending on the urgency of the situation. In our previous work, it has been extremely rare for an ACS patient to report active suicidality that requires intervention.

Upon enrollment, the RA will also conduct proactive safety planning with all participants in the following ways: (1) asking participants to identify 1-2 safety contacts that we would contact in the event that participants become at risk, (2) working with participants to identify the emergency department nearest to their home; (3) and instructing patients to go to this emergency room if they feel unsafe, and inform research staff once they are in a safe place (e.g., hospitalized or back at home). Participants will be asked to report any worsening symptoms to the interventionist during sessions, or in between sessions by contacting the study RA.

For enrolled participants, the PHQ-9 will be administered at baseline, post-intervention, and 3-month follow-up, which will allow us to monitor for worsening depression symptoms. The RA will review changes in participant's PHQ-9 scores over time and contact the participant to discuss any concerns, asking about their symptoms, needs, and concerns about staying in the study, and conducting an initial safety assessment as needed (as described above). The same procedures as described above will be followed if participants endorse suicidality on PHQ-9 item 9 when completing the measure as part of any of the surveys. REDCap will be set up to send automatic alerts to the study staff for any PHQ-9 item 9 responses greater than zero. Participants will be contacted within 24 hours.

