**d. Adverse event reporting guidelines**

All PHRC guidelines will be followed with respect to reporting unanticipated problems, including adverse events. Specifically, when a serious or non-serious adverse event occurs, the PI will review the event to determine if it was possibly or definitely related to participation in the research. For all unanticipated problems and adverse events deemed related or possibly related to the research, a member of the research team will complete and submit an Other Event report through Insight/eIRB as soon as possible and within 5 working days / 7 calendar days (as defined in the March 2014 Reporting Unanticipated Problems Including Adverse Events report). At Continuing Review, a summary of all unanticipated problems will be provided as per PHRC protocol. Finally, if there are unanticipated problems, especially if serious or recurrent, the PI will amend the protocol if it is deemed necessary to protect the safety and welfare of the participants.

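### Outside the mood and suicidality monitoring, adverse events are captured only when staff learn of them and no summary by arm is planned, so harms may be under-ascertained

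*Combined protocol and SAP*

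**What the plan says.** **General adverse events.** Section IX.b makes the principal investigator responsible for safety monitoring and states: "If study staff becomes aware of any adverse events, the event will be reported immediately to the PI". Under section IX.d, when a serious or non-serious event occurs, "the PI will review the event to determine if it was possibly or definitely related to participation in the research". A report to the ethics board then follows: "For all unanticipated problems and adverse events deemed related or possibly related to the research". For the periodic review, "At Continuing Review, a summary of all unanticipated problems will be provided as per PHRC protocol".

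**Mood and suicidality.** Section VII.d is much more active. For enrolled participants, "the PHQ-9 will be administered at baseline, post-intervention, and 3-month follow-up, which will allow us to monitor for worsening depression symptoms". The research assistant reviews score changes, a non-zero answer to PHQ-9 item 9 triggers an automatic alert, interventionists in both groups observe participants at each session, and participants are asked to report worsening. Section IX.c repeats the main elements.

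**Other sources.** Sections V.a and V.e list a Cardiac History and Symptoms survey and extraction from the electronic health record. The stated purpose of the extraction is medical and demographic variables and eligibility.

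**Outcomes and analysis.** Table 1 covers feasibility and acceptability, and its only harm-like entry is a pain rating for the blood-spot procedure. Table 2 lists exploratory measures, including PHQ-9 and HADS. Section VI.c describes no adverse-event analysis or listing.

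**The concern.** The participants have had an acute coronary syndrome and have elevated depression symptoms, so some hospital visits and cardiac events are to be expected during the study, whatever their cause. Meditation practice could also cause distress that a depression score does not register. None of these has a described route into the study data except a participant volunteering it or staff noticing it.

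That route is weakest where the information matters most. Someone who stops attending loses the weekly contact in which an event would come up, and after the last session nobody has scheduled session contact. Section VIII.b says the study will inform a later efficacy trial. If few or no events are recorded, the planners of that trial cannot tell whether few occurred or few were found. With no table by arm, they would not have even the known events in usable form.

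**Working it through.** The plan states no adverse-event rate and no power calculation (section VI.d), so there is no figure of its own to reproduce. The check has two parts.

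**1. What each source covers**

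| Type of event | Scheduled ascertainment described | Summary planned |
|---|---|---|
| Worsening depression, suicidality | Yes, both arms: PHQ-9 at three time points, item 9 alerts, session observation | Within-group change in score; no count of participants who worsen |
| Blood-spot pain | Yes, post-intervention survey | Table 1 mean rating |
| Hospital or emergency visit | None; record extraction not assigned to this | None |
| New cardiac event | None stated; cardiac survey not tied to events | None |
| Distress or other harm from the program | None as an event; could surface in sessions, post-session surveys, exit interviews or practice logs | None as an event |

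**2. How much zero recorded events would show**

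Inputs:
- Arm size *n*: 20 (N=40 in section VI.d, 1:1) or 25 (approximately N=50 in Aim 1, 1:1). The documents give both totals.
- True risk per participant *p* and capture fraction *c*: not in the documents. Assumed values are *p* = 5% and 10%, and *c* = 100%, 75% and 50%. Capture is taken to be independent and equal across participants.

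*Upper bound after zero recorded events.* With full capture the one-sided 95% bound is 1 − 0.05^(1/*n*). With capture *c*, this bounds *p* × *c*, so the bound on *p* is that value divided by *c*.

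- *n* = 20: 1 − 0.05^(1/20) = 13.9%. At *c* = 75%, 0.1391/0.75 = 18.5%; at *c* = 50%, 0.1391/0.50 = 27.8%.
- *n* = 25: 1 − 0.05^(1/25) = 11.3%. At *c* = 75%, 0.1129/0.75 = 15.1%; at *c* = 50%, 0.1129/0.50 = 22.6%.

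*Chance of recording at least one event in an arm*: 1 − (1 − *p* × *c*)^*n*.

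| *n* | *p* | *c* = 100% | *c* = 75% | *c* = 50% |
|---|---|---|---|---|
| 20 | 5% | 64% | 53% | 40% |
| 20 | 10% | 88% | 79% | 64% |
| 25 | 5% | 72% | 62% | 47% |
| 25 | 10% | 93% | 86% | 72% |

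For example, at 20 per arm and a true risk of 5%, falling from full to half capture raises the chance of an empty record from 36% to 60%.

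*Where contact is thin.* The program runs about 8 weeks and the 3-month follow-up adds about 13, so 13/(8 + 13) = 62% of that span has no scheduled session. The Table 1 benchmarks are met with 25% of post-intervention and 30% of follow-up assessments missing. At 20 per arm, that is 20 × 0.25 = 5 and 20 × 0.30 = 6 participants.

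**The case against.** The strongest reply is that the harm the protocol names as its main psychosocial concern is monitored actively, on a schedule and in the same way in both arms. That is correct. A reader who took IX.b alone to mean that every harm depends on chance awareness would be wrong.

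Other strong readings also fail:
- *Only events judged related count.* Section IX.d sends forward all unanticipated problems as well as events judged related or possibly related, and it has the principal investigator review each known event. An event that is not submitted is not thereby unrecorded.
- *The principal investigator assesses relatedness unblinded.* The documents do not mention blinding. Section V.a says "The interventionist will receive ongoing supervision and feedback from the PI or MBCT mentor", which makes knowledge of allocation likely, but that is an inference.
- *The MBCT practice logs bias detection between arms.* Only MBCT participants complete "home practice logs documenting the frequency of and the thoughts related to their weekly mindfulness practice". The logs are not described as a safety channel, both arms share the same session schedule and survey battery, and no difference in capture is shown. Nor does the plan set out a between-arm comparison of harms that could be biased.

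Three further replies carry some weight. The survey batteries went to the ethics board and are not reproduced here, so the cardiac survey may already ask about events. The follow-up survey and PHQ-9 do close the 3-month interval, for mood. And the 13.9% bound comes from sample size, so better capture cannot lower it. It only makes the full-capture figure the applicable one.

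What remains is that, outside mood and suicidality, the described method is passive, the available sources are not assigned to events, and no listing by arm is specified.

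**Conclusion.** The point holds in this limited form. General adverse events may be under-ascertained, most plausibly among participants who stop attending and after the last session, and the plan specifies no summary of them by arm. A record of zero events would leave an arm's risk bounded only at 13.9% (20 per arm) or 11.3% (25 per arm) with full capture. At an assumed 50% capture the bounds would be 27.8% and 22.6%. The full-capture bounds rest only on arm size. The others rest on capture fractions that the documents neither support nor contradict.

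A reader might infer that the pilot will understate harms or distort their comparison between arms. The documents do not go that far: the extent of missed events is unknown and no difference between arms is demonstrated. The feasibility and acceptability outcomes are defined without adverse-event counts and are unaffected. This is an inexpensive improvement to safety data meant to inform a larger trial.

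**What to change.** 1. Add the same short question to the post-intervention and 3-month surveys in both arms, covering any hospital or emergency visit, any new cardiac event, and any harm felt from the program or study procedures. Worsening mood needs no new item because the PHQ-9 is already given at both times. If the cardiac survey already asks about such events, designate it as the source instead of duplicating it.
2. Cross-check against the health-record data already being extracted, over the same window for every participant. This reaches people who return no survey. All participants are patients of the one health system, although care received elsewhere may not appear.
3. Report one descriptive table of all adverse events by arm, serious and non-serious, regardless of judged relatedness, with relatedness and source of report as columns. The source column shows separately any event known only from a practice log, which the control arm does not have.

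Ethics-board reporting rules stay unchanged. The cost is a few survey items, an added purpose for an existing extraction, and one table. The downside is more recorded events unrelated to the program, as expected in cardiac patients.

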**c. Outcomes monitoring**

Outcomes will be monitored via scores on self-report questionnaires at baseline, post-intervention, and 3-month follow-up. Participants will also be monitored during weekly MBCT and health enhancement control sessions. Study staff (licensed clinical psychologist, LCSW) will be available to respond to any worsening in outcomes. REDCap will be automated to inform the RA and PI of any endorsements of suicidality, so that the study team can follow up with these patients immediately.

**d. Adverse event reporting guidelines**

All PHRC guidelines will be followed with respect to reporting unanticipated problems, including adverse events. Specifically, when a serious or non-serious adverse event occurs, the PI will review the event to determine if it was possibly or definitely related to participation in the research. For all unanticipated problems and adverse events deemed related or possibly related to the research, a member of the research team will complete and submit an Other Event report through Insight/eIRB as soon as possible and within 5 working days / 7 calendar days (as defined in the March 2014 Reporting Unanticipated Problems Including Adverse Events report). At Continuing Review, a summary of all unanticipated problems will be provided as per PHRC protocol. Finally, if there are unanticipated problems, especially if serious or recurrent, the PI will amend the protocol if it is deemed necessary to protect the safety and welfare of the participants.

